8. STATISTICAL ANALYSIS METHODS

If not otherwise specified, statistical significance is defined as $p < 0.05$ and is two-tailed. Data will be summarized with respect to demographic and baseline characteristics and safety variables.

**NOVUM PHARMACEUTICAL RESEARCH SERVICES
STATISTICAL ANALYSIS PLAN**

Permethrin Cream, 5%

Protocol / Study No. 71675502

For categorical variables, the number and percentage of each category within a parameter will be calculated for non-missing data. For continuous variables, statistics will include n, mean, standard deviation, median, minimum and maximum values.

All statistical analyses will be conducted using SAS[®], Version 9.4 or higher. Datasets will be prepared using headings from Clinical Data Interchange Consortium (CDISC), Study Data Tabulation Model (SDTM) implementation for human clinical trials, and ADaM (Analysis Dataset Model).

8.1 Baseline Characteristics

8.1.1 Patient Disposition

The patient disposition information will be summarized by treatment. The number of patients randomized, treated with study medication will be tabulated by treatment. In addition, completion status and primary reason for withdrawal will be summarized by treatment.

8.1.2 Demographic and Other Baseline Characteristics

Baseline comparability of all treatment groups will be evaluated separately in the PP and Safety populations.

The following baseline demographics (determined from their initial study visit) will be evaluated:

- Age (years)
- Sex (male/female)
- Ethnicity (Hispanic/non Hispanic)
- Race (White, Black/African American, Native Hawaiian or Other Pacific Islander, Asian, American Indian or Alaska Native, Other)
- Baseline severity score of nocturnal itching
- Severity of lesion count infestation pretreatment (mild, moderate, severe)

Summary tables by treatment will be presented. Continuous variables will be summarized using descriptive statistics (n, mean, standard deviation, median, minimum, maximum). Categorical variables will be summarized using frequencies and percentage.

Baseline comparability of the treatments will be presented using Chi-square test for the categorical variables, and Analysis of Variance for the continuous variables.

All data will be listed by treatment and patient.

**NOVUM PHARMACEUTICAL RESEARCH SERVICES
STATISTICAL ANALYSIS PLAN**

Permethrin Cream, 5%

Protocol / Study No. 71675502

8.1.3 Medical History

At Visit 1 patients will be questioned about medical history, including acute and chronic medical history and medical history relevant to their scabies.

Medical history data will be listed by treatment and patient.

8.1.4 Concomitant Medications

All concomitant medication use within 6 months of Visit 1 and throughout the study will be recorded.

All prior and concomitant medications taken since screening until the end of the study will be listed by treatment and patient.

8.1.5 Pregnancy Test

All females of childbearing potential will have a urine pregnancy test performed at Visit 1 and Visit 3.

Pregnancy test results will be listed by treatment and patient.

8.2 Efficacy Analyses

8.2.1 Primary Efficacy Analysis

Bioequivalence with Clinical Endpoints Analysis

The proportion of patients in each treatment group with Therapeutic Cure is the primary efficacy endpoint of the study.

The Per Protocol (PP) Population will be used for the analysis of equivalence.

Based on the usual method used in OGD for binary outcomes, the 90% confidence interval for the difference in success proportions between test and reference treatment should be contained within [-0.20, +0.20] (or [-20%, +20%] in percent) in order to establish equivalence.

The compound hypothesis to be tested is:

$$H_0: P_T - P_R < -20\% \text{ or } P_T - P_R > 20\% \quad \text{versus}$$

$$H_A: -20\% \leq P_T - P_R \leq 20\%$$

**NOVUM PHARMACEUTICAL RESEARCH SERVICES
STATISTICAL ANALYSIS PLAN**

Permethrin Cream, 5%

Protocol / Study No. 71675502

where P_T = percent cure rate of test treatment
 P_R = percent cure rate of reference treatment.

Let

n_T = sample size of test treatment group
 cn_T = number of cured patients in test treatment group
 n_R = sample size of reference treatment group
 cn_R = number of cured patients in reference treatment group

$$\hat{P}_T = cn_T/n_T \quad \hat{P}_R = cn_R/n_R, \quad \text{and}$$

$$se = (\hat{P}_T (1 - \hat{P}_T)/n_T + (\hat{P}_R (1 - \hat{P}_R)/n_R)^{1/2}$$

where \hat{P}_T = estimated cure rate (%) of test treatment
 \hat{P}_R = estimated cure rate (%) of reference treatment.

The 90% confidence interval for the absolute difference between the proportions of patients in test and reference who are considered a therapeutic cure (primary) will be calculated as follows:

$$L = (\hat{P}_T - \hat{P}_R) - 1.645 se$$

$$U = (\hat{P}_T - \hat{P}_R) + 1.645 se$$

If the 90% confidence interval⁰ for the absolute difference between the proportion of patients who are considered a therapeutic cure (primary) in the Test and Reference groups is contained within the range [-20% + 20%] then bioequivalence of the Test product to the Reference product will be considered to have been demonstrated for the primary endpoint.

Sensitivity Analysis for Primary Efficacy Endpoint

As a sensitivity analysis, the primary efficacy analysis will be performed on the safety population using LOCF. This analysis will use LOCF such that subjects with no post-dose data will be considered as non-responders.

8.2.2 Supportive Analyses

The following supportive analyses will be performed for the primary endpoint:

1. The primary analysis will be performed including patients who completed Visit 2 within 14 ± 2 days and Visit 3 within 28 ± 4 days.

**NOVUM PHARMACEUTICAL RESEARCH SERVICES
STATISTICAL ANALYSIS PLAN**

Permethrin Cream, 5%

Protocol / Study No. 71675502

2. The primary analysis will be performed including patients who completed Visit 2 within 14 ± 2 days and Visit 3 between Day 26 and Day 32, inclusive.
3. The primary analysis will be performed including patients who completed Visit 2 within 14 ± 2 days and Visit 3 within 28 ± 2 days.

To declare therapeutic equivalence of the Test product to the Reference product, therapeutic equivalence must be demonstrated for only the primary analysis.

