The Guidance recommends a  $\pm 2$ -day window for both the Day 14 and Day 28 visits. This protocol incorporates a  $\pm 4$ -day window for both visits. The justification for the wider visit window is that permethrin cream 5% is expected to cure scabies infestation after a single treatment. That is, if it works by Day 14 it should still work by Day 28, and thus the re-infestation rate from Day 14 to Day 28 is expected to be low. Therefore, a wider visit window on Day 28 should be acceptable. The effect of different visit window durations at Day 14 and Day 28 will be explored in the three supportive analyses.

The Guidance also recommends that the youngest patient (with scabies infestation who meets the inclusion criteria) from each household is considered to be the index or primary patient of the household for evaluation of the primary endpoint, that other members of the household and close contacts are enrolled as secondary patients (not included in primary endpoint analysis) and evaluated for all safety parameters, and that secondary patients should receive the same study treatment as the

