#### Supportive Analyses:

The following supportive analyses will be performed for the primary endpoint:

1. The primary analysis will be performed including patients who completed Visit 2 within 14 ± 2 days and Visit 3 within 28 ± 4 days.
2. The primary analysis will be performed including patients who completed Visit 2 within 14 ± 2 days and Visit 3 between Day 26 and Day 32, inclusive.
3. The primary analysis will be performed including patients who completed Visit 2 within 14 ± 2 days and Visit 3 within 28 ± 2 days.

To declare therapeutic equivalence of the Test product to the Reference product, therapeutic equivalence must be demonstrated for only the primary analysis.

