5. SAMPLE SIZE

For the primary endpoint analysis (proportion of patients in the PP population who are considered to be a Therapeutic Cure on Day 28 ± 4), sample size is estimated for therapeutic equivalence of the Test to the Reference product.

Based on data from a previous bioequivalence study conducted to support approval of the first generic product of permethrin cream, 5%, the therapeutic cure rate (p_R) of the Reference product (Elimite™ permethrin cream 5%) is expected to be about 88% in the PP population. Assuming that the Therapeutic Cure rate for the Test group (p_T) is an absolute difference of 5% lower than the Reference group (i.e., $p_T - p_R = -5\%$), a sample size of 107 patients in each active group in PP population will provide at least 90% power to demonstrate therapeutic equivalence (i.e., the 90% confidence interval [Yates' continuity corrected] on $p_T - p_R$ is within a defined equivalence range [-20%, +20%]).

To allow for approximately 14 % of patients who may drop out from the study or are otherwise non-evaluable, approximately 250 patients (125 in each treatment group) will be randomized, such that there will be an estimated 214 patients (107 per group) in the PP population for statistical evaluation of therapeutic equivalence.

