7. STUDY POPULATIONS

Per-Protocol (PP) Population

The PP population will include:

- Met the inclusion/exclusion criteria as defined in this protocol at Visit 1.
- Did not take any prohibited medications throughout the study.
- Did not have any significant deviations from the protocol. Did not develop any concurrent dermatological condition or illness exhibiting symptoms similar to scabies, or symptoms that in the Investigator's opinion would interfere with endpoint assessments.
- Completed the last study visit (Visit 3) Day 28 ± 4.

Patients will be included in the PP population as treatment failures in the final analysis on Day 28 (provided they had no significant protocol deviations) if they 1) withdrew from the study because of lack of efficacy, 2) show therapeutic cure at Day 14 ± 4 but re-infestation at Day 28 ± 4, or 3) do not respond to the initial treatment and have new lesions or microscopic confirmation of mites, ova, or fecal matter on Day 14 ± 4.

Safety Population

The safety population will include all patients who are randomized who applied at least one dose of the assigned study product.

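### Read literally, the supportive visit-window analyses drop lack-of-efficacy withdrawals whom the per-protocol population counts as failures, so comparing them with the primary analysis mixes two changes

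*SAP*

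**What the plan says.** Protocol 8.3 acknowledges that the ±4-day windows are wider than the ±2 days in the FDA draft guidance and answers: "The effect of different visit window durations at Day 14 and Day 28 will be explored in the three supportive analyses".

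Protocol 11.6 and SAP 8.2.2 define those analyses in the same words. Analysis 1 is run "including patients who completed Visit 2 within 14 ± 2 days and Visit 3 within 28 ± 4 days". Analysis 2 is run "including patients who completed Visit 2 within 14 ± 2 days and Visit 3 between Day 26 and Day 32, inclusive". Analysis 3 keeps the Visit 2 condition and narrows Visit 3 to 28 ± 2 days. The notes to Tables T14.1.9.1 to T14.1.9.3 repeat these conditions. None of these places makes an exception for patients already classified as failures.

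The per-protocol (PP) definition in SAP 7 and Protocol 11.3.1 requires Visit 3 within Day 28 ± 4, but then adds a failure rule. Absent significant deviations, patients enter as failures if they "withdrew from the study because of lack of efficacy", if they were cured at Day 14 and re-infested at Day 28, or if they had not responded at Day 14. The first category does not rest on any Visit 3 finding.

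**The concern.** The primary analysis and the supportive analyses appear to treat the same patients differently. A patient who withdraws for lack of efficacy and has no visit in the window is a failure in the primary denominator. On the literal wording, that patient is absent from all three supportive denominators.

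The supportive analyses exist to show what the visit windows do. Analysis 1 is meant to differ from the primary only through the Visit 2 window. If it also loses known failures, agreement with the primary is not clean evidence that the wide window is harmless, and disagreement cannot be attributed to the window. At stake is how well the plan can defend its departure from the recommended windows, not the equivalence conclusion itself.

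**Working it through.** **Inputs.** Criterion, SAP 8.2.1: "90% confidence interval for the difference in success proportions between test and reference treatment should be contained within [-0.20, +0.20]", with a Wald interval and multiplier 1.645. Planning values, SAP 5: the Reference cure rate "is expected to be about 88% in the PP population"; the Test rate "is an absolute difference of 5% lower than the Reference group", so 83%; and "a sample size of 107 patients in each active group in PP population will provide at least 90% power". The documents give no count or forecast of lack-of-efficacy withdrawals, so every such count below is an assumption.

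**The plan's own figure.** With the Yates term 1/n that SAP 5 uses for sizing:

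- se = √[(0.88 × 0.12 + 0.83 × 0.17)/107] = 0.0480, and 1/107 = 0.0093.
- Power = Φ((0.15 − 0.0093)/0.0480 − 1.645) + Φ((0.25 − 0.0093)/0.0480 − 1.645) − 1 = 0.9005 + 0.9996 − 1 = 90.0%.

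The 107 per group reproduces (exact binomial enumeration gives 89.8%). Nothing in this point changes it.

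**Who is kept.**

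| Patient in the PP population | Primary | Analyses 1 to 3, read literally |
|---|---|---|
| Lack-of-efficacy withdrawal, no in-window visit | Failure | Dropped |
| Lack-of-efficacy withdrawal, both visits in window | Failure | Failure |
| Day 14 failure, both visits in window | Failure | Failure |
| Re-infestation, both visits in window | Failure | Failure |

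**Effect of dropping failures.** Removing failures leaves the cured count unchanged and shrinks the denominator, so each arm's cure rate rises. With d = P_T − P_R and se = √[P_T(1 − P_T)/n_T + P_R(1 − P_R)/n_R], the interval is d ± 1.645 se. All other patients are assumed to be in window, so that the effect of failure handling is seen alone.

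| Failures dropped (Test, Reference) | Test | Reference | Difference, points (90% CI) |
|---|---|---|---|
| 0, 0 (primary) | 80/107 = 74.8% | 94/107 = 87.9% | -13.1 (-21.7 to -4.4) |
| 5, 2 | 80/102 = 78.4% | 94/105 = 89.5% | -11.1 (-19.4 to -2.8) |
| 8, 2 | 80/99 = 80.8% | 94/105 = 89.5% | -8.7 (-16.9 to -0.6) |
| 3, 3 | 80/104 = 76.9% | 94/104 = 90.4% | -13.5 (-21.8 to -5.2) |
| 8, 7 | 80/99 = 80.8% | 94/100 = 94.0% | -13.2 |
| 10, 9 | 80/97 = 82.5% | 94/98 = 95.9% | -13.4 |

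The first row lies outside ±20 points. Losses of 5 and 2, or 8 and 2, bring the interval inside. Equal or nearly equal losses move the difference slightly further from zero. At rates near the planning assumption the shift is small: 89/107 v 94/107 gives -4.7 (-12.6 to 3.2), and dropping 4 Test and 3 Reference failures gives 89/103 v 94/104, -4.0 (-11.3 to 3.3).

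**Which comparisons are affected.** Analyses 1, 2 and 3 share the Visit 2 condition and the completer condition. Their Visit 3 windows are Days 24–32, 26–32 and 26–30. Comparing them with each other varies only the Visit 3 window, among completers. Comparing any of them with the primary also changes how failures are handled.

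**The case against.** The strongest reply is that the failure rule may be meant to carry over: each supportive analysis is described as the primary analysis, and Tables T14.1.9.1 to T14.1.9.3 are labelled per-protocol. That reading is possible, but SAP 8.2.2 does not state it, and two programmers could build different datasets from the same text. This part of the reply makes the defect an unstated rule; it does not remove it.

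Other parts of the reply stand, and they rule out stronger readings that a reader might infer:

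- *That the three analyses cannot isolate the windows at all.* The comparison among Analyses 1 to 3 on Visit 3 timing remains usable, among completers.
- *That every lack-of-efficacy withdrawal is lost.* Visit 3 doubles as the early termination visit (Protocol 10.5.3), and sites are to try to complete the end-of-study procedures (Protocol 10.3.5). Some withdrawals may have an in-window date, and the number without one may be small.
- *That the difference moves toward zero whenever the worse product loses more patients.* The 8 v 7 and 10 v 9 rows above contradict this.
- *That equivalence could be wrongly declared.* Both documents say that only the primary analysis must succeed. A passing supportive analysis rescues nothing.
- *That Day 14 failures should also be kept whatever their Visit 3 date.* Keeping those failures while dropping cures seen outside the window selects on outcome. Assume 25% of Visit 3 dates fall outside a narrower window in every group, and that 17 of 27 Test and 8 of 13 Reference failures were set at Day 14. One filter for all leaves the rates at 74.8% and 87.9%. Exempting the Day 14 failures gives 60/(60 + 17 + 7.5) = 71.0% and 70.5/(70.5 + 8 + 3.75) = 85.7%, a difference of -14.7 instead of -13.1.

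The plan also offers partial cover. The safety-population sensitivity analysis with LOCF (SAP 8.2.1) does not require Visit 3, Table T14.1.1 counts lack-of-efficacy terminations by arm, and Listing L16.2.5.1 shows visit dates. These let a reader bound the problem, but none of them isolates the Visit 2 window.

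**Conclusion.** The point holds in a limited form. As written, the supportive analyses omit lack-of-efficacy withdrawals without an in-window visit, whom the PP population retains as failures. The comparison with the primary, above all for Analysis 1, therefore mixes a window change with a change in failure handling. Cure rates rise in any arm that loses such patients, and the difference can move in either direction. In the illustrations it runs from -8.7 to -13.5 points, against -13.1 in the primary.

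Those sizes rest on assumed withdrawal counts and on cure rates chosen near the margin; the documents do not say how many patients are affected. Sample size and the equivalence decision are untouched. This is worth correcting because Protocol 8.3 relies on these analyses to examine the wider windows.

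**What to change.** In SAP 8.2.2, Protocol 11.6 and the notes to Tables T14.1.9.1 to T14.1.9.3:

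1. State that PP patients counted as failures because they withdrew for lack of efficacy stay in all three supportive analyses as failures, whether or not Visit 2 or Visit 3 took place in window.
2. For all other patients who attended Visit 3, apply the Visit 3 window equally, Day 14 failures included.
3. Report by arm how many cures and how many failures each filter removes.

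The cost is a short addition to the text, one changed selection flag, the removal counts, and slightly lower supportive cure rates. No new data are needed.

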8.2.3 Treatment-by-Site Interaction and Pooling of Clinical Sites

As this is a multiple-site study, the interaction of treatment-by-site may be evaluated for the primary efficacy endpoint in the PP population (for equivalence testing). The treatment-by-site interaction will be evaluated by the Breslow-Day test for homogeneity of the odds ratio at the 5% significance level ($p < 0.05$). A site(s) with a low enrollment rate(s) may be pooled with its geographically closest site, so as to avoid bias in the estimation of a treatment-by-site interaction effect. The pooling will be done for low enrolling sites that account for less than 4-7% of the total number of patients in the PP population at the site with the highest enrolling rate in the PP population. If the treatment-by-site interaction term is found to be statistically significant ($p < 0.05$) for the primary endpoint, then the interaction term will also be assessed for clinical relevance before pooling the data across sites. This will include examination of Therapeutic Cure rates at each site where sample sizes per treatment may be influential in the assessment of the interaction.

8.3 Safety Analysis

Safety analysis will be conducted on safety population.

8.3.1 Adverse Events

All the adverse events (AEs) reported throughout the study will be coded and classified according to the MedDRA (Medical Dictionary for Regulatory Activities) coding dictionary (Version 20.0 or higher). Each adverse event is to be evaluated for date of start and end, seriousness, severity, causal relationship with the study drugs, action taken and outcome.

All AEs will be listed by treatment and patient.

A summary table of the number and percent of patients with AEs by system organ class, preferred term, and treatment will be presented. Each patient will be counted only once within each preferred term.

**NOVUM PHARMACEUTICAL RESEARCH SERVICES
STATISTICAL ANALYSIS PLAN**

Permethrin Cream, 5%

Protocol / Study No. 71675502

A frequency summary table of the number of AEs by system organ class, preferred term, severity, and treatment will be presented. Severity will be classified as “Mild”, “Moderate”, or “Severe”.

Similarly, a frequency summary table of the number of AEs by system organ class, preferred term, and relationship to a study drug, and treatment will be presented. Relationship to a study drug will be classified as “Not Related” or “Related”.

Adverse event frequencies will be compared between treatments using Fisher’s exact test.

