#### ADVERSE REACTIONS

In clinical trials, generally mild and transient burning and stinging followed application with ELIMITE™ (permethrin) 5% Cream in 10% of patients and was associated with the severity of infestation. Pruritus was reported in 7% of patients at various times post-application. Erythema, numbness, tingling, and rash were reported in 1 to 2% or less of patients (see **PRECAUTIONS-General**). Other adverse events reported since marketing ELIMITE™ (permethrin) 5% Cream include: headache, fever, dizziness, abdominal pain, diarrhea and nausea and/or vomiting. Although extremely uncommon and not expected when used as directed (see **DOSAGE AND ADMINISTRATION**), rare occurrences of seizure have been reported. None have been medically confirmed as associated with ELIMITE™ treatment.

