2. OBJECTIVES

The objectives of this study are to:

1. Evaluate the therapeutic equivalence of the Test formulation, Permethrin Cream, 5% (Encube Ethicals) to the marketed product, Elimite™ Cream (permethrin) 5% (Prestium Pharma, Inc.) in patients with scabies.
2. Compare the safety of Test and Reference treatments in patients with scabies.

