8.4 Multiple Comparisons

No multiple comparison adjustment will be made in this study.

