OUTPUT: L:\DEV\755\71675502\SAS\OUT\XXXX
Page 1 of N

T14.1.11 Overall Summary of Adverse Events
(Safety Population)

Description	Test	Reference	Total
Subjects in Safety Analysis Set	xxx	xxx	xxx
Subjects with at least one AE	xxx (xx.x)	xxx (xx.x)	xxx (xx.x)
Discontinued study drug due to above AE	xxx (xx.x)	xxx (xx.x)	xxx (xx.x)
AEs reported	xxx	xxx	xxx
Mild	xxx (xx.x)	xxx (xx.x)	xxx (xx.x)
Moderate	xxx (xx.x)	xxx (xx.x)	xxx (xx.x)
Severe	xxx (xx.x)	xxx (xx.x)	xxx (xx.x)
Not Related	xxx (xx.x)	xxx (xx.x)	xxx (xx.x)
Related	xxx (xx.x)	xxx (xx.x)	xxx (xx.x)
Death	xxx (xx.x)	xxx (xx.x)	xxx (xx.x)
Serious AE	xxx (xx.x)	xxx (xx.x)	xxx (xx.x)

Test: Permethrin Cream, 5%, (Encube Ethicals)
Reference: Elimite™ Cream (permethrin) 5% (Prestium Pharma, Inc.)

Note: subjects having multiple AEs within same system organ class were counted only once in respective system organ class.
Under any event subjects having multiple AEs with same Preferred Term were counted only once within the respective preferred term.

T14.1.12 Summary of Frequency of Adverse Events by Body System
(Safety Population)

Body System	Preferred Term	Test N = xxx		Reference N = xxx		Fisher's p-value
		Events	Patients n (%)	Events	Patients n (%)	
Patients with at least one AE	Total	xx	xxx (xx.x)	xx	xxx (xx.x)	x.xxxx
Ear and labyrinth disorders	Ear pain etc.	xx	xxx (xx.x)	xx	xxx (xx.x)	x.xxxx
etc.						

Test: Permethrin Cream, 5%, (Encube Ethicals)

Reference: Elimite™ Cream (permethrin) 5% (Prestium Pharma, Inc.)

N= number of patients in safety population in that particular group; n= number of patient with data available for that particular group;
total % is based on N

PROGRAM: L:\DEV\755\71675502\SAS\PGM\XXXX
Created on: ddmmmyy hh:mm

OUTPUT: L:\DEV\755\71675502\SAS\OUT\XXXX
Page 1 of N

**T14.1.13 Summary of Frequency of Adverse Events by Relationship
(Safety Population)**

Body System	Preferred Term	Test # of Events (N = xxx)		Reference # of Events (N = xxx)	
		Related n (%)	Not Related n (%)	Related n (%)	Not Related n (%)
Total AEs	Total	xxx (xx.x)	xxx (xx.x)	xxx (xx.x)	xxx (xx.x)
Ear and labyrinth disorders	Ear pain	xxx (xx.x)	xxx (xx.x)	xxx (xx.x)	xxx (xx.x)
	Hypoacusis	xxx (xx.x)	xxx (xx.x)	xxx (xx.x)	xxx (xx.x)

Test: Permethrin Cream, 5%, (Encube Ethicals)

Reference: Elimate™ Cream (permethrin) 5% (Prestium Pharma, Inc.)

N = Total number of events in that particular group group; Percentage is based on total number of events.

PROGRAM: L:\DEV\755\71675502\SAS\PGM\XXXX

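### Safety is a study objective, but the only planned between-arm safety inference is a Fisher p-value; without a Test–Reference difference and interval, a non-significant result cannot bound excess harm

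*SAP*

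**What the plan says.** SAP section 2 gives the second objective as "Compare the safety of Test and Reference treatments in patients with scabies"; Protocol section 9.0 has the same objective. The analysis that serves it is in SAP 8.3.1, which summarises AEs by arm, by severity and by relationship, and then states "Adverse event frequencies will be compared between treatments using" Fisher's exact test. SAP section 8 sets the general rule that "statistical significance is defined as $p < 0.05$ and is two-tailed", and SAP 8.4 adds "No multiple comparison adjustment will be made in this study".

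The shells in SAP section 9 show what will be printed:

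- T14.1.11 has patients with any AE and discontinuations by arm. Relationship and severity sit under the row for AEs reported.
- T14.1.12 has events, patients n (%) and a column headed "Fisher's p-value", overall and by term.
- T14.1.13 and T14.1.14 (relationship and severity) use the number of events as the denominator.
- T14.1.15 counts serious AEs, and T14.1.16 describes vital signs.

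None of these has a column for a difference between arms or for an interval. Protocol 11.8 adds neither; it makes the Fisher test conditional on there being enough data and allows a similar test in its place.

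The insert in Protocol Appendix C (Adverse Reactions) reports that "generally mild and transient burning and stinging followed application with ELIMITE™ (permethrin) 5% Cream in 10% of patients".

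**The concern.** A difference test that fails to reach significance cannot separate products that are alike from a sample too small to show that they differ. The plan recognises this for efficacy, where SAP 8.2.1 requires a 90% confidence interval inside ±20 points rather than a non-significant test. For safety it provides only the difference test. If the Fisher p-value exceeds 0.05, the planned output does not say what excess reaction rate on Test remains compatible with the data. That is the information a reader needs from a safety comparison of a generic with its reference product.

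**Working it through.** **Inputs**

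- Arm size: SAP section 5 says "approximately 250 patients (125 in each treatment group) will be randomized". SAP section 7 says "The safety population will include all patients who are randomized who applied at least one dose of the assigned study product". So the safety comparison has at most about 125 per arm.
- Test: Fisher's exact, two-sided, 5% (SAP 8 and 8.3.1).
- Reference rate: 10% for burning and stinging (Protocol Appendix C).
- Test rates of 15%, 20% and 25%: assumptions. The documents give no Test rate.

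**The plan's own figure.** The documents state no power or precision for safety; the sizing is for efficacy only. It reproduces. With cure rates of 83% and 88% and 107 per group, se = √[(0.83×0.17 + 0.88×0.12)/107] = 0.0480. The Yates term is 1/107 = 0.0093. Power = Φ[(0.20 − 0.05 − 0.0093)/0.0480 − 1.645] + Φ[(0.20 + 0.05 − 0.0093)/0.0480 − 1.645] − 1 = 90.0%. Then 107/(1 − 0.14) = 124.4, rounded up to 125 per group.

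**Power of the safety test.** Power is the sum, over all pairs of counts (x, y) with two-sided Fisher p below 0.05, of Bin(x; n, p_T) × Bin(y; n, p_R), with n = 125 and p_R = 10%:

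| Assumed Test rate | Fisher power |
|---|---|
| 15% | 17% |
| 20% | 53.8% |
| 25% | 85% |

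A doubling would thus be missed 46% of the time at 125 per arm. If fewer patients were dosed, power for 10% vs 20% would be 51.6% at 120 per arm, 50.2% at 115 and 46.6% at 107. About 199 per arm would be needed for 80% power by the uncorrected formula, or 219 with continuity correction.

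**What an interval adds.** Take 20/125 (16.0%) on Test and 12/125 (9.6%) on Reference.

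- Fisher p = 0.18.
- Difference = 0.160 − 0.096 = 0.064.
- se = √(0.160×0.840/125 + 0.096×0.904/125) = √(0.001075 + 0.000694) = 0.0421.
- 95% Wald interval = 0.064 ± 1.96×0.0421, or -1.8 to +14.6 points.

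A second case shows how much a p-value can conceal. 23/125 vs 12/125 gives p = 0.067, while the Newcombe 95% interval for the 8.8-point difference is +0.1 to +17.5 points.

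**Precision available without more patients.** The 95% half-width at 125 per arm is 1.96×√(2×0.10×0.90/125) = 7.4 points if both rates are 10%, and 1.96×√[(0.20×0.80 + 0.10×0.90)/125] = 8.8 points at 20% vs 10%.

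**Can the intervals be derived from the shells?** For any AE and for a single term, yes, from n and N in T14.1.12. For related AEs, no: T14.1.13 counts events, and T14.1.11 puts the related row under AEs reported, so the number of patients with a related AE is not clearly printed. For burning and stinging together, no: if they are coded as separate terms, a patient with both appears in two rows, and the rows cannot be added.

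**The case against.** The best defence is that descriptive safety reporting is usual in a trial sized for efficacy, and that this plan does more than print p-values. Incidence, severity, relationship, serious AEs and vital signs are all shown by arm. That is correct. A reader might infer that safety is compared by p-values alone, or that the second objective goes unanswered. The documents do not support either: side-by-side incidence tables are a comparison, and what is missing is the estimate of the difference and its uncertainty.

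A reader might also infer that the plan treats p > 0.05 as proof of comparable safety. No passage says so. There is no safety margin or decision rule, and the equivalence claim rests on the primary efficacy analysis alone. The point is about what the planned output can support.

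The scenario is also open to challenge. The 20% rate is assumed, the insert's 10% comes from other trials, and larger differences are well covered (power 85% for 10% vs 25% and about 98% for 10% vs 30%). This stands, and is why a range is shown. The insert's figure also covers burning and stinging together, whereas the plan tests by preferred term, so the planned test may never address that composite.

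Finally, it is tempting to extend the argument to the insert's 7% pruritus rate and to erythema. Protocol 11.8 rules that out: scabies signs and symptoms are not AEs unless they worsen enough that the patient is dropped and given alternative therapy. Itching is an entry criterion and a rated symptom, and the insert's precautions list pruritus and erythema among the accompaniments of infestation. AE counts for these terms would not measure what the insert measured, and an interval on them could reassure falsely. Pruritus is already tabulated by arm and visit in T14.1.10, in the per-protocol population.

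**Conclusion.** The gap is real and modest. Safety comparison is an objective, the sole inferential tool is a two-sided Fisher test, and no difference or interval is planned. At 125 per arm the test would detect a doubling from 10% to 20% about 54% of the time, so non-significance does not exclude an excess that many would want to know about; in the worked example the upper limit is +14.6 points. The size rests on three assumptions: about 125 dosed patients per arm, the insert's 10% applying to Reference in this trial, and a hypothetical Test rate. The absence of an interval depends on none of them. This is a cheap reporting improvement that should be made; it is not an arithmetic error, and it does not affect the equivalence decision.

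**What to change.** In SAP 8.3.1 and shells T14.1.11 and T14.1.12:

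1. Report the Test–Reference difference in the percentage of patients, with a 95% interval (for example Newcombe), for any AE, for any related AE counted by patient, and for burning and stinging grouped under a definition fixed in advance.
2. Base any statement on relative safety on these intervals, and label the Fisher p-values descriptive.
3. Do not add AE-table intervals for pruritus or erythema, given the AE definition in Protocol 11.8.
4. While editing, align Protocol 11.8 (test if data suffice) with SAP 8.3.1 (test without condition).

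The cost is a few table rows, one term grouping and a little programming. It needs no new data, patients or safety margin. Protocol 11.1 has the SAP finalised before database lock, and SAP section 4 releases the randomization schedule to the statistician only after lock, so a change made before lock is made blind. If lock has passed, the intervals should be added and identified as specified afterwards.
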